### 11.3 Serious Adverse Events

Serious adverse event collection begins after randomization and study procedures have been initiated. If a patient experiences a serious adverse event after consent, but prior to randomization or starting study procedures, the event will NOT be collected. Study site personnel must alert the VCC of any **serious and study procedure related** adverse event within 24 hours of awareness of the event regardless of suspected causality. The site Investigator must sign off on the initial report within three (3) days of study team's awareness of the SAE. Alerts issued via telephone are to be immediately followed with official notification on the adverse event case report form. See Appendix C for reporting timelines for serious, unexpected, study related events (SAEs) and serious, unexpected suspected adverse reactions (SUSARs)

As per the FDA and NIH definitions, a serious adverse event is any adverse event that results in one of the following outcomes:

- Death
- A life-threatening experience (that is, immediate risk of dying)
- Prolonged inpatient hospitalization or re-hospitalization

As per <http://www.fda.gov/Safety/MedWatch/HowToReport/ucm053087.htm>: Report if admission to the hospital or prolongation of hospitalization was a result of the adverse event. Emergency room visits that do not result in admission to the hospital should be evaluated for one of the other serious outcomes (e.g., life-threatening; required intervention to prevent permanent impairment or damage; other serious medically important event).

- Persistent or significant disability/incapacity

As per <http://www.fda.gov/Safety/MedWatch/HowToReport/ucm053087.htm>: Report if the adverse event resulted in a substantial disruption of a person's ability to conduct normal life functions, i.e., the adverse event resulted in a significant, persistent or permanent change, impairment, damage or disruption in the patient's body function/structure, physical activities and/or quality of life.

Reportable serious adverse events that may not result in death, be life-threatening, or require hospitalization may be considered serious adverse events when, based upon appropriate medical judgment, they may jeopardize the patient and may require medical or surgical intervention to prevent one of the outcomes listed in this definition.

Serious adverse events will be collected through **Study Day 16 (or 48 hours after completion of the study drug administration)**, regardless of the investigator's opinion of causation.

## **12. Data and Safety Monitoring Board (DSMB)**

The principal role of the DSMB is to assure the safety of participants in the trial. They will regularly monitor data from this trial, review and assess the performance of its operations with respect to:

- Review of adverse events
- Review of every death occurring on study
- Interim results of the study for evidence of efficacy or adverse events
- Possible early termination of the trial because of new external information, early attainment of study objectives, safety concerns, or inadequate performance
- Possible modifications in the clinical trial protocol
- Performance of individual centers

The DSMB will consist of members with expertise in acute infections, acute lung injury, emergency medicine, biostatistics, ethics, and clinical trials. Appointment of all members is contingent upon the absence of any conflicts of interest. All the members of the DSMB are voting members. The unblinded statistician will be responsible for the preparation of all DSMB and adverse event reports and may review unblinded data. The DSMB will develop a charter and review the protocol and sample consent form during its first meeting. Subsequent DSMB meetings will be scheduled in accordance with the DSMB Charter with the assistance of the VCC. When appropriate, conference calls may be held in place of face-to-face meetings. Recommendations to end, modify, or continue the trial will be prepared by the DSMB executive secretary. Recommendations for major changes, such as stopping the trial, will be communicated immediately. Other recommendations will be distributed in writing to the VCC and sIRB, which will distribute with instructions for reporting to local IRBs when appropriate.

We will comply with the principles and approaches espoused by the NIH NHLBI guidance found here:

<https://www.nhlbi.nih.gov/grants-and-training/policies-and-guidelines/nhlbi-policy-data-and-safety-monitoring-extramural-clinical-studies>

## 13. APPENDICES

### Appendix A. Schedule of Events

#### Schedule of Events

Description:	Date of Randomization	Days 1-14	Days 15-16	Day 29
Confirmation of SAR-CoV-2 positive test result	X			
Home medications	X			
Verification of Inclusion/Exclusion Criteria	X			
Remote consent	X			
Randomization	X			
IP shipped to subject	X			
Self-Administered Dosing		X		
Self-Reported Symptom Survey		X	X	X
Assessment of Adverse Events		X	X	X
Modified COVID Ordinal Outcome Scale		X	X	X
Ventilator Status		X	X	X
ICU Status		X	X	X
Oxygen Status		X	X	X
Hospital Length of Stay		X	X	X
Vital Status				X
End of Study				X

## **Appendix B. Potential medication interactions with lopinavir/ritonavir**

Medications considered to present a potential interaction with lopinavir/ritonavir, which if ordered during the 14-day study period, will prompt study personnel to discuss with treating clinicians the risk-benefit assessment of this medication and potential need for additional monitoring: flecainide, mefloquine, methotrexate, mexilitine, rifampicin, rifapentine, amiodarone, cimetidine, dofetilide, phenobarbital, phenytoin, or sotalol, propafenone, astemizole, terfenadine, alfuzosin, apalutamide, ranolazine, dronedarone, rifampin, lurasidone, cisapride, pimozide, ergot-containing medicines (including dihydroergotamine mesylate, ergotamine tartrate, methylergonovine), lovastatin, simvastatin, lomitapide, sildenafil, triazolam, midazolam, rivaroxaban, fluticasone and anticoagulants or St. John's Wort.

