### 3.2 Exclusion Criteria

1. Prisoner
2. Pregnancy
3. Breast feeding
4. Two individuals from the same household are not enrolled in the study
5. Unable to randomize within 6 days after onset of acute respiratory infection symptoms
6. Hospitalization within the 6 days prior to randomization
7. Inability to swallow oral medications
8. Refusal or inability to be contacted and participate in daily symptom/safety monitoring in English or Spanish during the two-week follow-up period
9. Previous enrollment in this trial
10. Known severe chronic kidney disease requiring dialysis
11. Known liver disease (cirrhosis or  $>3$  times upper limit of normal for AST or ALT in medical record if available)
12. Known hepatitis B or hepatitis C infection
13. Known history of jaundice
14. Current heavy alcohol use, defined as 8 drinks or more per week for women or 15 drinks or more per week for men
15. Known seizure disorder

16. Known HIV infection
17. Known history of pancreatitis
18. Known history of prolonged QT interval (Long QT Syndrome, patient report, or QTc >500 milliseconds on most recently available electrocardiogram within the past 2 years)
19. Receipt of >1 dose of hydroxychloroquine, chloroquine, or lopinavir/ritonavir in the 10 days prior to enrollment
20. Known allergy to lopinavir/ritonavir
21. Currently prescribed (with planned continuation) or planned administration during 14-day study period of medication at high risk for QT prolongation as follows:  
*Antiarrhythmics:* Amiodarone, disopyramide, dofetilide, dronedarone, flecainide, ibutilide, procainamide, propafenone, quinidine, sotalol  
*Anti-cancer:* Arsenic trioxide, oxaliplatin, vandetanib  
*Antidepressants:* Amitriptyline, citalopram, escitalopram, imipramine  
*Antimicrobials:* azithromycin, ciprofloxacin, clarithromycin, erythromycin, fluconazole, levofloxacin, moxifloxacin, pentamidine, hydroxychloroquine  
*Antipsychotics:* alopoperidol, chlorpromazine, droperidol, olanzapine, pimozide, quetiapine, thioridazine, risperidone, ziprasidone  
*Others:* cilostazol, cimetidine, cisapride, donepezil, methadone, ondansetron, sumatriptan

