### 3.3 Justification of Exclusion Criteria

Since this is intended as an outpatient trial, patients hospitalized within 6 days prior to enrollment/randomization are excluded. The other exclusion criteria are primarily designed for patient safety. In addition to excluding specific vulnerable populations (e.g., prisoners), these criteria are designed to exclude patients for whom receipt of lopinavir/ritonavir might increase the risk of serious adverse events. Lopinavir/Ritonavir has been routinely prescribed to outpatients with HIV-1 without extensive cardiac workups, laboratory testing, or monitoring. In addition, we have incorporated guidelines for safe outpatient prescribing of lopinavir/ritonavir without a baseline electrocardiogram or outpatient cardiac monitoring and have put into place a method of monitoring newly prescribed medications during the 14-day intervention period.

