### **4.5 On-Study Monitoring**

All participants enrolled in the study will be outpatients (not hospitalized) and therefore initial monitoring will be remote as part of routine outpatient clinical care with treating physicians and nurses (we anticipate primarily virtual care/telehealth or routine telephone follow-up). The research staff will provide additional remote monitoring through daily electronic collection of symptoms, healthcare utilization, clinically obtained electrocardiograms, newly prescribed medications, and adverse event reporting with supplemental telephone follow-up as needed. The research team may flag potential issues but will defer specific decisions about additional care and hospital transfer to usual outpatient clinical care.

Lopinavir/ritonavir has been used extensively for outpatient treatment of other conditions without the need for additional monitoring during short term therapy.

Between baseline and Study Day 15, study personnel will ascertain and review the initiation of any new medications daily and evaluate for potential medication interactions with lopinavir/ritonavir (see Appendix B). If a medication that is considered to be contraindicated with lopinavir/ritonavir is discovered, site physician investigator or designee will contact the patient to discuss if stopping study drug is appropriate or if the medication in question may be stopped or substituted in consultation with the prescribing/treating clinician. If a medication with a potential interaction with lopinavir/ritonavir is identified, study personnel will contact the treating clinician to ensure they are aware of the potential interaction, as needed. Treating clinicians will determine whether an alternative medication would be

appropriate or whether the risk-benefit ratio favors continuing the medication with the known potential interaction.

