#### **4.6 Criteria for Stopping Study Drug**

We will stop administration of the blinded study drug temporarily or permanently for (a) adverse events without evidence of an alternative cause to the patient's symptoms, (b) results of on-study monitoring, or (c) clinical deterioration if requested by treating clinician.

If a patient experiences an adverse event that the patient treating clinicians, or investigators feel merits temporarily or permanently stopping the study drug, we will stop the study drug. We will record the explanation for stopping the study drug in the case report form, and we will record and report the adverse event according to the adverse event guidelines below. If the adverse event resolves to the extent that the patient, treating clinicians, and investigators feel that resuming the study drug is appropriate, we will resume the study drug, and we will record this information in the case report form.

If an EKG is obtained as part of routine clinical care after enrollment and the QTc is greater than or equal to 500 ms, we will discontinue the study drug, unless a repeat EKG after at least 24 hours demonstrates the QTc is less than 500 ms, at which time we will direct the patient to resume the study drug. We will record both the value for the QTc and the decision to continue or stop the study drug in the case report form. If the daily on-study monitoring by study personnel for medication interactions indicates a potential interaction with a medication that treating clinicians feel is required for the optimal treatment of the patient and with which treating clinicians and the investigator feel it would be unsafe to administer lopinavir/ritonavir, we will stop study drug and record the reason in the case report form.

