### Telephone/Videophone Data Collection:

While primary data collection will be by electronic methods as above, specific circumstances will trigger telephone or videophone follow-up, based on the following:

- Participant does not complete daily electronic data collection for two consecutive days.
- Participant does not complete Study Day 29 assessment
- Identification of newly prescribed medication if deemed necessary by site investigator.
- New electrocardiogram

- Lack of administration of study medication, if unable to confirm plan to resume study medication
- Hospitalization
- Reported adverse events, if deemed necessary by the site investigator
- Clarification or concern by study team
- By request of participant

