Important potential risks include PR prolongation at therapeutic dosing, and QT prolongation with supratherapeutic doses. Lopinavir/ritonavir interacts with several drugs since it is an inhibitor of the P450 isoform CYP3A and is likely to increase the plasma concentration of drugs that are metabolized by CYP3A4. Therefore, LPV/r should not be co-administered with drugs primarily metabolized by CYP3A and for which elevated plasma concentrations are associated with serious and/or life-threatening events. A list of such products is included in the lopinavir/ritonavir label. Rare reports of second- or third-degree atrioventricular block in patients with underlying structural heart disease and pre-existing conduction system abnormalities, or in patients receiving drugs known to prolong the PR interval such as verapamil, have been reported in patients receiving lopinavir/ritonavir. Lopinavir/ritonavir should be used with caution in such patients. In addition, QT prolongation with supratherapeutic doses and when lopinavir/ritonavir is co-administered with drugs known to prolong the QT interval has been reported. Because lopinavir/ritonavir is principally metabolized by the liver, caution should be exercised when administering this drug to patients with impaired hepatic function. Extra monitoring is recommended when diarrhea occurs. The relatively high frequency of diarrhea during treatment with lopinavir/ritonavir may compromise the absorption and efficacy (due to decreased compliance) of lopinavir/ritonavir or other concurrent drugs. Serious persistent vomiting and/or diarrhea with lopinavir/ritonavir use might also compromise renal function. The safety of lopinavir/ritonavir for treatment of patients with COVID-19 disease is unknown. COVID-19 may be associated with cardiac effects. lopinavir/ritonavir may prolong QT at supratherapeutic doses and prolong PR at therapeutic doses, resulting in arrhythmias.

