## **11. ADVERSE EVENTS**

Assuring patient safety is an essential component of this protocol. Lopinavir/ritonavir is approved by the Food and Drug Administration and there is an have been used in clinical practice for decades with a well-established safety profile. Use of lopinavir/ritonavir for the treatment of acute respiratory infection due to COVID-19, however, raises unique safety considerations. This protocol addresses these considerations through:

1. Exclusion criteria designed to prevent enrollment of patients likely to experience adverse events with receipt of lopinavir/ritonavir
2. On-study monitoring of co-interventions (e.g., newly prescribed medications) and patient characteristics (e.g., healthcare utilization, clinically obtained electrocardiogram) to intervene before adverse events occur.
3. Systematic collection of safety outcomes relevant to use of lopinavir/ritonavir in this setting.

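### Appendix B, the list cited for judging newly started medicines, omits 33 of the 42 QT-risk medicines that exclusion 21 bars at entry

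*Protocol*

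**What the plan says.** Protocol Section 3.2 has two medication exclusions, repeated in the Section 1 summary. Both cover continuing use and use planned within the 14-day study period. Exclusion 21 lists medicines by class that the protocol regards as high risk for QT prolongation. Exclusion 22 lists other medicines that must not be combined with the study drug.

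After enrolment, Section 4.5 has study personnel look daily, from baseline to Study Day 15, for any newly started medication and "evaluate for potential medication interactions with lopinavir/ritonavir (see Appendix B". Appendix B is the only list cited there. Its function is that a listed medicine, if ordered during the 14 days, "will prompt study personnel to discuss with treating clinicians the risk-benefit assessment of this medication" and any extra monitoring that may be needed.

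The protocol leans on this step in several places:

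- Section 3.3, when explaining why no baseline electrocardiogram is needed, adds that the investigators "have put into place a method of monitoring newly prescribed medications during the 14-day intervention period".
- Section 11 counts among its safety measures "On-study monitoring of co-interventions (e.g., newly prescribed medications) and patient characteristics", with the aim of acting ahead of any adverse event.
- Section 9.1.2 acknowledges that QT prolongation "when lopinavir/ritonavir is co-administered with drugs known to prolong the QT interval has been reported".

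**The concern.** A medicine judged risky enough to bar entry should also be flagged if it is first prescribed on day 3. Exclusion 21 removes continuing and planned use, so unplanned new starts are left to the on-study review. If the list behind that review leaves out most of the exclusion 21 medicines, the review followed as written does not prompt for them.

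Little else is systematic. The trial is remote, and Section 9.2 explains that electrocardiogram testing is not required. The QTc stopping rule in Section 4.6 begins "If an EKG is obtained as part of routine clinical care after enrollment", so it depends on a test done for other reasons and acts only once the interval is already long. Telephone follow-up of a new medicine (Section 6) is triggered by "Identification of newly prescribed medication if deemed necessary by site investigator", which is discretionary. What is at stake is participant safety. No sample size, power or type I error figure is involved.

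**Working it through.** No figure in the plan needs reproducing; the check is a name-by-name comparison of three lists.

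**Inputs.** Exclusions 21 and 22 from Protocol Section 3.2, and the full text of Appendix B. Each name in the two exclusions was looked up in Appendix B. In exclusion 22, ergot-containing medicines count as one entry.

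**Exclusion 21 against Appendix B**

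| Class | Named in exclusion 21 | Also in Appendix B | Not in Appendix B |
|---|---|---|---|
| Antiarrhythmics | 10 | 6 (amiodarone, dofetilide, dronedarone, flecainide, propafenone, sotalol) | 4 |
| Anti-cancer | 3 | 0 | 3 |
| Antidepressants | 4 | 0 | 4 |
| Antimicrobials | 9 | 0 | 9 |
| Antipsychotics | 9 | 1 (pimozide) | 8 |
| Others | 7 | 2 (cimetidine, cisapride) | 5 |
| **Total** | **42** | **9** | **33** |

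- Named: 10 + 3 + 4 + 9 + 9 + 7 = 42.
- In Appendix B: 6 + 0 + 0 + 0 + 1 + 2 = 9, and 9/42 = 21%.
- Not in Appendix B: 4 + 3 + 4 + 9 + 8 + 5 = 33, and 33/42 = 79%.

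The antimicrobial row is missing in full: "azithromycin, ciprofloxacin, clarithromycin, erythromycin, fluconazole, levofloxacin, moxifloxacin, pentamidine, hydroxychloroquine". Ondansetron is among the five missing under others. The first antipsychotic on the exclusion list, whose name is printed unusually, is absent from Appendix B under any spelling.

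**Exclusion 22 against Appendix B.** All 18 of 18 entries are present; none is missing.

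**Reading the two results together.** One exclusion list was carried into the monitoring list whole and the other mostly was not. Neither Section 4.5 nor Appendix B refers back to exclusion 21, so nothing in the monitoring text supplies the missing names.

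**Are such prescriptions foreseeable?** The protocol itself expects some of them. Section 6.2 records receipt of azithromycin and of open-label hydroxychloroquine during follow-up, and Section 4.4 leaves other treatment to the treating clinician. Section 9.1.2 lists nausea and vomiting among the common reactions to the study drug, so a new ondansetron prescription is plausible. That last step is inference; the documents give no prescription rates.

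**The case against.** The counts are not in dispute. The case against concerns what they mean.

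*Section 4.5 has a second, stronger route.* When a contraindicated medicine is found, the site physician or designee contacts the patient about stopping study drug, or about stopping or replacing the medicine. A medicine that bars enrolment is a natural candidate. This narrows the gap but does not close it: the clause names no list and does not mention exclusion 21. The exclusion 22 medicines also bar enrolment, yet they were placed in Appendix B.

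*Appendix B is a reference, not a filter.* Staff must review every new medicine, and the interaction stopping rule in Section 4.6 is not confined to listed names. This stands. A new medicine outside the list is still seen and may be acted on; what is missing is a prompt that requires it.

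*The 42 names are already in the protocol.* True, and staff apply them at baseline. But they are written as an entry criterion, with no pointer to them for use on study. Azithromycin and hydroxychloroquine are also named in the Section 6.2 assessments, but as data to record, not as triggers for an interaction review.

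*Appendix B may be meant only for metabolic interactions.* The protocol does not say so, and the appendix already holds nine exclusion 21 medicines. If that was the intention, the QT-risk group has no on-study list at all.

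*Section 3.3 also relies on prescribing guidelines.* It does. Those guidelines are not in the documents, so what they require for new QT-prolonging co-medication cannot be judged here.

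*The 79% overstates the problem.* It gives equal weight to medicines with very different chances of being started. The three anti-cancer medicines would usually be planned, and so already excluded. Without them the count is (33 − 3)/(42 − 3) = 30/39 = 77%. The objection that this is not a measure of exposure stands in full.

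*Other safeguards exist.* A new electrocardiogram or a hospitalization triggers a call (Section 6), and the DSMB can ask for more monitoring (Section 9.2). Section 9.1.2 also links QT prolongation to doses above the therapeutic range. These are real but partial: none prompts a review when one of the 33 medicines is first prescribed.

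**Conclusion.** The concern holds. Appendix B leaves out 33 of the 42 medicines in exclusion 21 (79%) and none of the 18 entries in exclusion 22. For those 33, the on-study safeguard rests on someone recognising the medicine, not on the list that Section 4.5 cites. This matters because the protocol itself classes these medicines as high risk, acknowledges the interaction and requires no electrocardiogram.

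The conclusion assumes that Appendix B is used as written and that no other working list exists; the documents cite none. It makes no claim about how often these medicines would be started or that any participant was harmed. It is a change that should be made on safety grounds, with partial backups already in place, and it does not bear on the efficacy analysis.

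**What to change.** Either add the 33 missing medicines to Appendix B, which takes its coverage of exclusion 21 from 9/42 to 42/42, or have Section 4.5 and Appendix B state that any exclusion 21 medicine newly started on study prompts the Section 4.5 review. At the same time, mark which entries follow the contraindicated route and which the potential-interaction route. That assignment is a clinical judgment for the investigators. Section 4.4 needs no change.

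The cost is a revised appendix or one cross-reference, plus an updated list in the monitoring form. The downside is more prompts for staff to review. The sample size and the analysis are unaffected.
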